6. STUDY DESIGN

This is a randomized, controlled, open-label, parallel group, multi-center, 5-week pilot study to determine changes in BOE in adult smokers allowed *ad libitum* use of VBM-FG2 relative to adult smokers who are not allowed use of VBM-FG2. The data collected from this study will be used to estimate the variability of differences in the percent change from Baseline to the EOS in urinary total NNAL between Test and Control Groups; these findings will be used to estimate the sample size for a future pivotal study. This study will be conducted in approximately 150 adult

smokers who are considered to be in overall good health. Subjects will be randomized (based on gender, daily cigarette consumption [<20 and 20], and quit attempts [any quit attempts/no quit attempts]) to Test (allowed VBM-FG2 use) or Control (not allowed VBM-FG2 use) product in a 3:2 ratio (90 subjects randomized to Test: 60 subjects randomized to Control) with no more than a 60:40 distribution of either males or females to either group.

Screening	Baseline Period*		Product Use Period ^t			
Visit 1	Visit 2	Visit 3	Visit 4	Visit 5	Visit 6	Visit 7
Day -28 to Day -1	Day 1	Day 8±1	Day 15 ± 1	Day 22 ± 1	Day 29± 1	Day 36 ± 1
Subject evaluated against inclusion and exclusion criteria for study eligibility	Baseline CPD data gathered using recall of previous week and daily IVRS call.		Randomization in a 3:2 ratio (Test:Control) 
 • Test = ad libitum VBM-FG2 • Control = no VBM-FG2 			
Enrollment		Randomization				

*Baseline Period = after the daily IVRS call on Day 1 through the daily IVRS call on Day 8.

^t Product Use Period = after the daily IVRS call on Day 8 through the daily IVRS call on Day 36.

Note: Subjects in both groups are allowed to smoke their regular brand cigarettes during the entire study period

Expected duration of the study, from first subject first visit through last subject last visit is approximately 3 months. Expected duration for each subject is expected to be up to approximately 5 weeks (potentially 9 weeks from Screening to EOS). All subjects will be informed that they are allowed to smoke their own cigarettes or to quit smoking during the study.

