11.3.2 Secondary Endpoints

The secondary outcome measures or endpoints are:

- Differences in all BOE during the Baseline Period between Day 1 (weekly recall) versus Day 8 (daily tracking using IVRS).
- Difference in CPD during the Baseline Period between once weekly recall (Days 1 and 8) versus daily tracking (average of recordings on Days 2 through 8).
- Differences in the percent change from Baseline to EOS in BOE (urinary NE, S-PMA, blood COHb, exhaled CO) and CPD between the Test and Control Groups.
- Differences from Baseline to EOS in all BOE and CPD between the Test and Control Groups.
- Proporation of subjects in subgroups based on cigarette consumption change from Baseline to EOS (no change, <50% reduction, 50% reduction, 100% reduction, increase) within and between the Test and Control Groups.
- Proporation of subjects in subgroups based on total NNAL change from Baseline to EOS (no change, reduction, increase) within each group.
- Changes from Baseline (Day 8) to EOS in total scores of Fagerstrom Test for Cigarette Dependence (see Appendix 1), within and between the Test and Control Groups.
- Changes from Baseline (Day 1) to EOS on the Quit Attempts and Quitting Intentions, within and between the Test and Control Groups.

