11.4.1 Statistical Analyses of Primary Endpoint

A linear mixed model for repeated measures analysis of variance will be used for the analysis of the primary outcome measure. SAS procedure Proc Mixed will be used for the statistical computing. The null hypothesis is that smokers allowed *ad libitum* use of VBM-FG2 discs (test) will not differ in the primary biomarker (percent change from baseline to EOS in urinary total

NNAL) compared to smokers not allowed use of VBM-FG2 discs (control). The alternative hypothesis is that smokers allowed *ad libitum* use of VBM-FG2 discs will differ in the primary biomarker compared to smokers not allowed use of VBM-FG2 discs. The model will include percent (or absolute) change from baseline to EOS in urinary total NNAL as a response variable, product, visit, and product by visit interaction as fixed effects; and subject as random effect. In the expanded model, several additional factors will be considered. Details about the models are as follows:

Model 1:

Percent (or absolute) change from baseline in total NNAL = study group + visit + study group*visit + subject + random error

Model 2:

Percent (or absolute) change from baseline in total NNAL = study group + visit + study group*visit + subject + CPD + sex + race + body mass index (BMI) + age + random error

where

CPD = fixed covariate representing average number of cigarettes per day for past week from IVRS

study group = fixed effect term (test or control)

sex = fixed effect (male or female)

race = fixed effect (White or Non-White)

BMI = fixed effect covariate

age = fixed effect covariate (continuous)

visit = fixed effect term representing days (ordinal categorical variable)

subject = random subject effect

baseline = Total NNAL measure at Day 8

If the study group*visit interaction term is not statistically significant (P-value > 0.10), then the interaction term will be removed from the model and all comparisons will be done using the overall product means. If the interaction effect is significant (P-value < 0.10), then the comparisons will be conducted for each study visit. Comparisons between products will be done based on 5% level of significance.

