11.4.2 Statistical Analyses of Secondary Endpoints

Difference in baseline:

Paired T Test will be used to examine the difference in all 5 BOEs between Day 1 and Day 8.

Paired T test will also be used to examine the differences in CPD between the once weekly recall at Day 8 (from questionnaire) and the average daily tracking of CPD from Days 2 through 8 (from IVRS).

Difference in change from baseline:

Linear mixed model for repeated measures analyses of variance will be used for the analyses of the secondary outcome measures: percent change from baseline and absolute change from baseline in all other BOEs. The same model will be used for percent change from baseline and absolute change from baseline in CPD and Total score of FTCD, the model details are as follows:

For other BOEs:

Model 1:

Percent (or absolute) change from baseline = study group + visit+ study group*visit + subject + random error

Model 2:

Percent (or absolute) change from baseline = study group+ visit+ study group*visit + subject + CPD + sex + race + BMI + age + random error

For CPD and Total Score ofFTCD:

Model 1:

Percent (or absolute) change from baseline = study group+ visit+ study group*visit +subject+ random error

Model 2:

Percent (or absolute) change from baseline = study group+ visit+ study group*visit +subject+ sex + race + BMI + age + random error

where

CPD = fixed effect covariate representing average number of cigarettes per day for the past two days from IVRS

study group = fixed effect term (test or control)

sex = fixed effect (male or female)

age = fixed effect covariate (continuous)

race= fixed effect (White or Non-White)

BMI = fixed effect covariate (continuous)

visit= fixed effect term representing days (ordinal categorical variable)

subject = random effect

baseline = Day 8 value for BOE and average of Day 2 to 8 for CPD (IVRS)

If the study group*visit interaction term is not statistically significant (P-value > 0.10), then the interaction term will be removed from the model and all comparisons will be done using the overall product means. If the interaction effect is significant (P-value < 0.10), then the comparisons will be conducted for each study visit.

Least squared mean and standard error for the product effect will be estimated by study group and visit with p-values for statistical significance. P-value will also be provided for other effects in the model.

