All secondary and exploratory analyses will be conducted on the Per-protocol population only.

A linear regression analysis will be conducted within each group at each timepoint to examine the relationships between levels of all 5 BOEs (dependent variable) with either weekly cigarette counts (Day 1 and 8 from questionnaire) or daily cigarette counts (from IVRS) (independent variable). For total NNAL, the corresponding daily cigarette counts from IVRS will be the average of past 7 days. For other biomarkers, it will be the average of past 2 days. The regression analysis will be conducted on the Per-protocol population.

The proportion of subjects in subgroups will be provided with proportion and sample size based on:

- 1) Cigarette consumption change from Baseline (average of Days 2 to 8 from IVRS) to the last week (no change, <50% reduction, 2::50% reduction , 100% reduction, increase);
- 2) Total NNAL change from Day 8 to the last visit (no change, reduction, increase);
- 3) Total scores of FTCD change from Day 8 to the last visit (increase, no change, decrease)
- 4) Proportion of subjects in subgroups based on Changes from Baseline (Day 1) to EOS (increase, no change, decrease) on the change in Quit Attempts from Day 1 to last visit.
- 5) Proportion of subjects in subgroups based on Changes from Baseline (Day 1) to EOS (yes to no, no to yes, and same) on the change in Quitting Intentions from Day 1 to last visit.

The Mantel-Haenszel Chi-Square Test will be used for (1), (2), (3), and (4); Fisher exact test will be used for (5) to test the frequency differences between the two groups.

Additional statistical analyses:

Wilcoxon signed rank test will be used to test the FTCD score difference between the 2 baseline measures (Visit 2 and 3) for the test group. If there is no statistical significance, the average score will be related to the average amount of VBM-FG2 in the past week via linear regression. Otherwise the FTCD score for Visit 3 will be used.

For the test group only, a simple linear regression model will be used to examine the relationship between COHb and Exhaled CO at each post-baseline visit.

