A stepwise multiple linear regression model will also be used to examine the relationship between each of the 5 BOEs (response variable) and a number of factors including average CPD, average VBM-FG2 use, average use of other products, age, sex, BMI and race at each post-baseline visit for the test group only. The average amount of tobacco product use will be for the past 7 days when total NNAL is the dependent variable and will be for the past two days when other BOE is the dependent variable.

Demographics and Characterization of Tobacco Product Use and Exposure Patterns

Demographic baseline characteristics will be summarized by study group with descriptive statistics. For continuous data, descriptive statistics will include N, mean, median, SD, min, max, coefficient of variation (CV%), and 95% confidence interval (CI). For categorical data, frequency counts and percentages will be presented. Fisher's exact test will be used to test for the differences in categorical variables (sex, race: White versus Non-white, quit attempt, cigarette consumption per day: ≤ 20 and > 20) between the 2 study groups and t test, to test for the differences in continuous variables (age, body weight, height, BMI, Number of times stopped smoking cigarettes for 24 hours or longer in an attempt to quit in past 6 months, Number of years smoked since turning 21 years).

Descriptive statistics will be provided to summarize the use of all tobacco products including cigarettes, VBM-FG2 discs and other products by study group and visit. The mean for each variable will be plotted by study group over time.

For subjects in the test group, a simple linear regression model will be used to examine the relationship between visit average of CPD (from IVRS) and visit average of VBM-FG2 use for all post-baseline visits in the study.

For subjects in the test group, a frequency table will be provided with the responses (definitely would buy and probably would buy) in the VBM-FG2 Potential Purchase Interest Questionnaire as the row variable and their average VBM-FG2 use level (4 discs versus < 4) in the last 2 visits as the column variable. Fisher exact test will be used to test for the association.

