APPENDIX 2: LIST OF TFLS FOR INTERIM AND FINAL ANALYSES

Following is the list of TFLs that will be produced during the interim analyses.

- Table 14.1-1 Summary of Subject Disposition
- Table 14.1-2 Summary of Screening Demographics
- Table 14.1-3 Summary of Baseline Smoking Characteristics
- Table 14.2.1-3.1 Individual Data and Summary Statistics of S-PMA
- Table 14.2.1-3.2 Individual Data and Summary Statistics of Change from Baseline S-PMA
- Table 14.2.1-3.3 Individual Data and Summary Statistics of Percent Change from Baseline S-PMA
- Table 14.2.1-4.1 Individual Data and Summary Statistics of Carboxyhemoglobin
- Table 14.2.1-4.2 Individual Data and Summary Statistics of Change from Baseline Carboxyhemoglobin
- Table 14.2.1-4.3 Individual Data and Summary Statistics of Percent Change from Baseline Carboxyhemoglobin
- Table 14.2.1-5.1 Individual Data and Summary Statistics of Exhaled Carbon Monoxide
- Table 14.2.1-5.2 Individual Data and Summary Statistics of Change from Baseline Exhaled Carbon Monoxide
- Table 14.2.1-5.3 Individual Data and Summary Statistics of Percent Change from Baseline Exhaled Carbon Monoxide
- Table 14.2.1-6.1 Individual Data and Summary Statistics of Cigarettes per Day
- Table 14.2.1-6.2 Individual Data and Summary Statistics of Change from Baseline Cigarettes per Day
- Table 14.2.1-6.3 Individual Data and Summary Statistics of Percent Change from Baseline Cigarettes per Day
- Table 14.2.1-7.1 Individual Data and Summary Statistics of Total Score of Fagerstrom Test for Cigarette Dependence
- Table 14.2.1-7.2 Individual Data and Summary Statistics of Change from Baseline Total Score of Fagerstrom Test for Cigarette Dependence
- Table 14.2.1-7.3 Individual Data and Summary Statistics of Percent Change from Baseline Total Score of Fagerstrom Test for Cigarette Dependence
- Table 14.2.1-X Individual Data and Summary Statistics of Urine Creatinine (Interim only)
- Table 14.2.1-8.1 Individual Data and Summary Statistics of VBM-FG2 Discs per Day

- Table 14.2.1-8.2 Individual Data and Summary Statistics of Change from Baseline VBM-FG2 Discs per Day
- Table 14.2.1-8.3 Individual Data and Summary Statistics of Percent Change from Baseline VBM-FG2 Discs per Day
- Listing 16.2.8-12 Other Tobacco or Nicotine Containing Product Use Questionnaire by Subject
- Table 14.2.1-12 Individual Data and Summary Statistics for Number of Quit Attempts with Change from Baseline

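### Change in number of quit attempts is tested between groups only by its sign, so the size of the change goes unused and no between-group estimate is planned

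*SAP*

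**What the plan says.** SAP 11.3.2 lists as a secondary endpoint "Changes from Baseline (Day 1) to EOS on the Quit Attempts and Quitting Intentions, within and between the Test and Control Groups". Section 11.2 sets Day 1 as baseline and Day 36 as the follow-up.

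The variable is held as a number. Appendix 2 lists Table 14.2.1-12, "Individual Data and Summary Statistics for Number of Quit Attempts with Change from Baseline". The demographics part of 11.4.2 includes among its continuous variables "Number of times stopped smoking cigarettes for 24 hours or longer in an attempt to quit in past 6 months", with a t test between groups at baseline.

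The between-group test of change is item (4) of the subgroup list in 11.4.2, which sorts subjects by "increase, no change, decrease) on the change in Quit Attempts from Day 1 to last visit". The test is then named: "The Mantel-Haenszel Chi-Square Test will be used for (1), (2), (3), and (4".

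The full-scale mixed models are in 11.4.1 for total NNAL and in 11.4.2 for the other biomarkers, and then: "The same model will be used for percent change from baseline and absolute change from baseline in CPD and Total score of FTCD". Quit attempts are in none of them.

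**The concern.** Reducing the change to increase, no change or decrease scores one extra attempt and five extra attempts alike. For the other outcomes categorised this way, little is lost because a full-scale analysis stands beside the categories. For quit attempts the categories carry the whole comparison.

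Two things are at stake. The comparison may be less sensitive than the collected data allow. It also ends in a P value on three signs, with no planned estimate of how many more or fewer attempts the Test Group made. For a pilot meant to inform a pivotal study, such an estimate with its interval is the more useful output.

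**Working it through.** **1. Analyses side by side**

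| Outcome | Full-scale between-group analysis of change | Categorised test (11.4.2) |
|---|---|---|
| CPD | Mixed model, 11.4.2 | Item (1) |
| Total NNAL | Mixed model, 11.4.1 | Item (2) |
| FTCD total | Mixed model, 11.4.2 | Item (3) |
| Quit attempts | None | Item (4) |
| Quitting intentions | Not applicable (yes/no) | Item (5), Fisher |

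The t test on number of attempts compares the groups at baseline, not on change. Table 14.2.1-12 is descriptive.

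**2. Inputs**

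- Group sizes, from SAP section 6: "90 subjects randomized to Test: 60 subjects randomized to Control", so N = 150.
- Level: two-sided 5%. Section 11.4.1 says "Comparisons between products will be done based on 5% level of significance" for the primary comparison. That it applies here, and is two-sided, is an assumption.
- Attempt rates, dispersion and recall windows for the change: not in the SAP, so all are assumptions. There is no stated power figure to reproduce.

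**3. Statistics compared**

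Let d be the end-of-study count minus the Day 1 count. The planned test is Q = (N - 1)r², where r is the correlation of group with sign(d), scored -1, 0, 1; Q is referred to chi-square on 1 df. The alternative is the rank-sum test on d.

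**4. Normal-limit check (difference of 0.5 SD, assumed)**

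SE = √(1/60 + 1/90) = 0.1667 SD.

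- Full scale: 0.5/0.1667 = 3.00; power = Φ(3.00 - 1.96) = 85%.
- Sign only, efficiency 2/π: 0.5 × √(2/π) = 0.399; 0.399/0.1667 = 2.39; power = Φ(0.43) = 67%.

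This is the loss for a continuous change. Counts with many zeros lose less.

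**5. Comparable recall windows**

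Counts are Poisson with a gamma-distributed subject rate shared by both visits, and Day 1 mean equal to the Control mean (6,000 trials per setting):

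| Control mean, Test mean | Sign test | Rank-sum | Gain (points) |
|---|---|---|---|
| 0.1, 0.3 | 47.9% | 51.3% | 3.4 |
| 0.2, 0.45 | 43.0% | 46.8% | 3.8 |
| 0.3, 0.6 | 42.1% | 47.0% | 4.9 |
| 0.5, 0.9 | 43.6% | 50.2% | 6.6 |
| 1, 1.6 | 46.1% | 55.5% | 9.4 |
| 3, 4.2 | 53.9% | 68.7% | 14.8 |

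A separate simulation of ten settings (Control mean 0.3-2, Test 1.5-2 times Control, gamma shape 0.5-2; 2,000 trials each) gave sign-test power of 42-81% and rank-sum power of 48-90%. Gains ran from 6 points (42% to 48%) to 15 points (57% to 72%).

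With strong extra variation within subjects the gain shrank to 2-4 points (for example 20.0% to 23.6% at means 1 and 2). If both visits ask about a rolling six months, the windows overlap; the gain was then about 0.5-6 points, because only 2-18% of subjects change by more than one attempt.

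**6. End-of-study window much shorter than Day 1**

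The only window the SAP states for attempts is six months, for a baseline item. Day 1 to Day 36 is 35 days. With a six-month baseline and a 36-day follow-up count (shape 0.5-1, six-month mean 0.5-2, Test rate 2-3 times Control; 3,000 trials each), the rank-sum test had lower power than the planned test in 11 of 12 settings. The difference ran from -3 to +1 points.

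Adjusting for the Day 1 count does help here. With Day 1 mean 1 and end-of-study means 0.2 and 0.4, power was 15.6% for the sign test, 15.1% for rank-sum on change, and 49.4% for a linear ANCOVA of the end-of-study count on the Day 1 count. In a more variable case (0.2 and 0.5) the figures were 15.2%, 14.3% and 27.0%.

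**7. Error rate and choice of estimate**

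Under no difference, rejection was 4.5-5.2% for all tests. The Hodges-Lehmann difference was exactly 0 in 98-100% of trials at means 0.3 and 0.6 (shape 1) and 0.5 and 1 (shape 0.5), and in 92% at 1 and 1.6 (shape 0.5), because of tied counts.

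**The case against.** The strongest reply is that an ordered three-category test on a sparse, recalled count is a defensible choice. It is valid at its level, the SAP claims no power, the study is a pilot about NNAL variability, and quit attempts come last among many secondary endpoints. All of that stands, and it limits the point to a minor one.

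Three stronger readings are tempting, and the documents do not support them.

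- *A rank test on the change is more powerful whatever the recall window.* The SAP does not state the window for the Day 1 to Day 36 change. If the follow-up window is much shorter, the change is dominated by baseline variation and the gain disappears (step 6).
- *The plan gives no information on the number of attempts.* Table 14.2.1-12 summarises the number and its change, and section 12 promises means and 95% CIs by study group for continuous secondary endpoints at the interim. What is missing is a planned between-group difference with its interval. The shells for the final tables are not at hand.
- *The planned test is wrong.* It holds its error rate; the criticism is of efficiency and of the missing estimate.

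**Conclusion.** The point holds as a minor improvement. Between-group change in quit attempts is a named secondary endpoint held as a number, and its only between-group test uses the sign of the change, without a between-group estimate.

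The power cost depends on assumptions that the SAP cannot settle: about 5-15 points against a rank-sum test for moderate counts with comparable windows, 2-4 points for rare or very variable counts, and essentially nothing if the end-of-study window is much shorter. In that last case the gain comes from adjusting for the Day 1 count. Section 11.4.2 restricts secondary analyses to the per-protocol population, so actual numbers will be below 90 and 60 and all power figures somewhat lower. At an assumed 72 and 48, the rank-sum gain was still about 7-12 points in three comparable-window settings.

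**What to change.** In SAP 11.4.2, keep item (4) as a descriptive frequency table and drop its Mantel-Haenszel test. Make the between-group comparison on the count:

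- If the Day 1 and end-of-study questions use the same recall window, apply a Wilcoxon rank-sum test to the change in number of attempts.
- If the windows differ, compare the end-of-study count adjusted for the Day 1 count, for example by rank ANCOVA or a negative binomial model. The gain shown above is for a linear ANCOVA; these two forms were not simulated.
- Report the between-group difference in means, or the rate ratio from the count model, with its 95% CI. Do not use the Hodges-Lehmann estimate, which will often be 0.

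State the recall window at each visit in the same place, since it decides between the first two.

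The cost is a sentence or two in the SAP and a few lines of code, on data already collected. The result is slightly harder to read than three percentages, which the frequency table still shows.

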5.3 Secondary Objectives

The secondary objectives of this study are to:

- Compare the difference in BOE (urinary total NNAL, nicotine metabolites, S-phenylmercaptmic acid [S-PMA], blood carboxyhemoglobin [COHb], and exhaled carbon monoxide [CO]) and CPD between two methods for determining CPD during the Baseline Period:
 - Recall of average daily CPD for prior week using Past 7 Day Cigarettes Use Questionnaire (Day I).
 - Daily CPD tracking using an IVRS (7 day average of values recorded on Days 2 through 8).
- Compare the differences in percent change in urinary nicotine equivalent (NE), S-PMA, blood COHb, exhaled CO, and CPD from Baseline to EOS between adult smokers randomly assigned to Test Group (*ad libitum* VBM-FG2 use) and Control Group (no VBM-FG2).
- Compare the changes in all BOE and CPD from Baseline to EOS between Test Group and Control Group over 4 weeks.
- Characterize subgroups based on change in CPD from Baseline to EOS (no change, <50% reduction, ≥50% reduction, 100% reduction, increase) within each study group.
- Characterize subgroups based on change in total NNAL from Baseline to EOS (no change, reduction, increase) within each study group.
- Compare changes in the Fagerstrom Test for Cigarette Dependence (FTCD) from Baseline (Day 8) to EOS within and between each study group.
- Compare changes on the Quit Attempts and Quitting Intentions from Baseline (Day I) to EOS within and between each study group.

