- Table 14.2.1-13 Frequency and Percentage of Subjects with Change from Baseline in Quitting Intentions
- Table 14.3.1-1 Summary of Product-Emergent Adverse Events
- Table 14.3.1-2 Frequency of Product-Emergent Adverse Events (All Causalities)
- Table 14.3.1-3 Frequency of Product-Emergent Adverse Events by Severity (All Causalities)
- Table 14.3.1-4 Frequency of Product-Emergent Adverse Events (Possibly, Likely, or Definitely Related to Study Product)
- Table 14.3.1-5 Frequency of Product-Emergent Adverse Events by Severity (Possibly, Likely, or Definitely Related to Study Product)
- Table 14.3.2-2 Serious Adverse Events

The TFLs that will be produced during the final analyses (all subjects) have been provided in the accompanying TFL shells document.

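### Quitting intentions: the planned three-way change table pools steady intenders with steady non-intenders, leaves Day 1 intention unused, and has no within-group test or interval although a within-group comparison is an objective

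*SAP*

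**What the plan says.** Section 5.3 of the SAP lists this secondary objective: "Compare changes on the Quit Attempts and Quitting Intentions from Baseline (Day I) to EOS within and between each study group". Section 11.3.2 restates it as an endpoint: "Changes from Baseline (Day 1) to EOS on the Quit Attempts and Quitting Intentions, within and between the Test and Control Groups".

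Section 11.4.2 gives the method. Item (5) classifies each subject as "yes to no, no to yes, and same) on the change in Quitting Intentions from Day 1 to last visit" and reports proportions with sample sizes. The test is then named: "Fisher exact test will be used for (5) to test the frequency differences between the two groups". Items (1) to (4), which include the parallel quit-attempts item (increase, no change, decrease), get a Mantel-Haenszel chi-square test instead.

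The only listed output specific to quitting intentions is in Appendix 2: "Table 14.2.1-13 Frequency and Percentage of Subjects with Change from Baseline in Quitting Intentions". The analysis set is also fixed in section 11.4.2: "All secondary and exploratory analyses will be conducted on the Per-protocol population only". Section 6 sets the upper limit on numbers: "3:2 ratio (90 subjects randomized to Test: 60 subjects randomized to Control".

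**The concern.** A subject who said yes on Day 1 can only stay at yes or move to no. A subject who said no can only stay at no or move to yes. Day 1 intention thus decides which change is possible. Item (5) discards it by placing both kinds of unchanged subject in one category. Two groups can then show the same three-way table while their switching rates differ.

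The second problem is a mismatch within the document. The objective and the endpoint both speak of a comparison within each group, but the method names only a test between groups.

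At stake is whether the trial can say, with an effect size and an interval, if access to the product changes intention to quit. As planned, it would give proportions and one p-value.

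**Working it through.** **Inputs.** From the SAP: three categories, Fisher's exact test, at most 90 Test and 60 Control subjects, and a 5% level (stated in section 11.4.1 for product comparisons; two-sided use here is assumed). The SAP gives no power for this endpoint, so there is no planned figure to reproduce. It also gives no share of yes answers on Day 1 and no switching rates, so all of those below are assumptions.

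**1. What the three-way table measures.** Let b be the share answering yes on Day 1, p the yes-to-no rate among them, and q the no-to-yes rate among the rest. The cells are:

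- yes to no: b × p
- no to yes: (1 − b) × q
- same: b(1 − p) + (1 − b)(1 − q)

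Each cell depends on b, and b cannot be recovered from the three cells.

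**2. Constructed example.** Take yes-to-no / same / no-to-yes counts of 9/63/18 in 90 Test subjects and 6/42/12 in 60 Control subjects. Both groups are 10% / 70% / 20%, so Fisher's p = 1.00. Now let Day 1 yes be 60 of 90 in Test and 30 of 60 in Control.

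| | Test | Control |
|---|---|---|
| yes to no | 9/60 = 15% | 6/30 = 20% |
| no to yes | 18/30 = 60% | 12/30 = 40% |

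- Mantel-Haenszel odds ratio for yes at end of study, stratified by Day 1 answer: (51×6/90 + 18×18/60) / (9×24/90 + 12×12/60) = 8.8/4.8 = 1.83, 95% CI 0.86 to 3.92.
- Cochran-Mantel-Haenszel (CMH) test: observed minus expected is (51 − 50) + (18 − 15) = 4, with variance 2.81 + 3.81 = 6.62. Chi-square = 16/6.62 = 2.42, p = 0.12.

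The result is not significant, but it is an estimate in one direction where the planned table shows no difference at all.

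**3. Power, consistent shift.** Simulation with 81 and 54 subjects (10% loss assumed), no-to-yes 40% against 20% and yes-to-no 15% against 30%, Test against Control:

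| Day 1 yes | Fisher, planned | Ordered Mantel-Haenszel (−1/0/+1) | CMH stratified by Day 1 |
|---|---|---|---|
| 30% | 46% | 55% | 66% |
| 50% | 39% | 48% | 62% |
| 60% | 36% | 47% | 59% |

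At 50% Day 1 yes the cells are 7.5 / 72.5 / 20% in Test and 15 / 75 / 10% in Control. The pooled category hardly differs between groups.

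**4. Power, other patterns.** Simulation with 90 and 60 subjects, Day 1 yes at 30% / 50% / 70%:

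| Assumed pattern | Fisher | Ordered | Stratified |
|---|---|---|---|
| Smaller consistent shift (yes-to-no 10% v 20%, no-to-yes 35% v 20%) | 33/29/28% | 41/38/37% | 49/47/44% |
| Only no-to-yes differs (40% v 20%; yes-to-no 20% in both) | 44/30/16% | 37/20/11% | 46/27/13% |
| Both transitions higher in one arm (35% v 15%) | 69/69/69% | 14/4/14% | 19/4/18% |

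The last row has a simple cause. With 50% yes on Day 1, the end-of-study share is 0.5×0.65 + 0.5×0.35 = 50% in Test and 0.5×0.85 + 0.5×0.15 = 50% in Control, so there is no net shift for a directional test to find.

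**5. Type I error.** With equal rates in both arms, all three tests reject in 4.5% to 5.1% of trials at 90/60.

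**6. Within-group part.** Set beside sections 5.3 and 11.3.2, section 11.4.2 offers proportions per category and names no paired test and no interval for the change. This gap is separate from the pooling: McNemar's test needs only the two off-diagonal counts, which item (5) does report. In the example these are 18 against 9 in Test (net change +9/90 = 10 points) and 12 against 6 in Control (+6/60 = 10 points).

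**The case against.** The strongest defence is that an unordered test suits an objective that names no direction. That stands in part. A reader might infer that the planned test is the weakest choice or loses power in general. The results in step 4 do not support this: Fisher's test beats the ordered test when only one transition differs, is within about 4 points of the stratified test there, and is far ahead when both transitions rise in one arm.

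A reader might also infer that direction is lost. It is not. Yes-to-no and no-to-yes are separate categories with reported proportions; only the p-value ignores their order. Nor does the ordered test in items (1) to (4) make item (5) an error, since nothing in the SAP requires the items to match.

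Ignoring Day 1 intention does not make the test invalid. Intention is measured before randomisation, and the simulated error rates confirm this. The example in step 2 depends on a Day 1 imbalance (67% against 50%) that was chosen to make the point. Such an imbalance is possible, because intention is not among the randomisation factors in section 6 and the analysis is per-protocol, but nothing shows that it will occur.

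Finally, to say that the within-group comparison is never made would go too far. Proportions by direction of change are planned, and the final table layouts are in a separate shell document that is not at hand. What remains is that the SAP text names no within-group test or interval. The same gap applies to quit attempts, which share the same objective.

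**Conclusion.** The concern holds in limited form. Item (5) merges two opposite states into one category, leaves a recorded baseline answer unused, and supplies no formal within-group analysis for an objective worded as within and between groups. The pooling and the missing within-group method follow from the SAP text and rest on no assumption.

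The cost in power is conditional. For a consistent shift in one direction it is about 39% against 62% (23 points) at 81/54 with 50% yes on Day 1, and about 16 to 18 points for the smaller shift at 90/60. All rates and the 10% loss are assumed. For other patterns the loss is absent, small or reversed.

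Severity is low. This is a secondary endpoint in a pilot meant to estimate NNAL variability, no power is claimed for it, and neither the primary result nor the sample size of the later study depends on it.

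**What to change.** Amend item (5) of section 11.4.2 as follows.

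- Report the full 2×2 table of Day 1 by end-of-study intention for each group.
- Within each group, give McNemar's test and a 95% CI for the change in the proportion intending to quit. Name a within-group analysis for quit attempts as well.
- Between groups, compare end-of-study intention stratified by Day 1 intention (CMH), or by logistic regression with Day 1 intention as a covariate, and report an odds ratio with a 95% CI.
- Keep the three-category Fisher test as a supportive analysis.

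The cost is some SAP wording and one changed table, with no new data. The drawback is that the stratified test is insensitive to transitions that rise in both directions, which is why the Fisher test should stay.
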